8.4.6 Pregnancy

- Details of all pregnancies in female patients and female partners of male patients and exposure during breastfeeding will be collected after the start of study drug and until 60 days after the last dose of NL-201 and 120 days after the last dose of pembrolizumab, or 30 days following cessation of study treatment if the patient initiates new anti-cancer therapy must be reported by the investigator.
 - If a participant inadvertently becomes pregnant while on study treatment the participant will be immediately discontinued from study treatment.
- If a pregnancy is reported, the Investigator should inform the Sponsor within 24 hours of learning of the pregnancy and should follow the procedures outlined in [Section 10.4](#).
- Abnormal pregnancy outcomes (eg, spontaneous abortion, fetal death, stillbirth, congenital anomalies, ectopic pregnancy) are considered SAEs.

8.5 Reporting and Treatment of Overdose

Any overdose of the Sponsor's product, as defined below, should be reported to the Sponsor within 24 hours of awareness, regardless if associated with clinical symptoms or abnormal laboratory results.

For this study, any dose of NL-201 greater than 20% of target dose within a 24-hour time period will be considered an overdose.

In the event of an overdose, the Investigator should:

1. Contact the Medical Monitor immediately.

2. Consider standard supportive therapy including, if necessary, hospitalization for observation and monitoring.
3. Closely monitor the patient for any AE/SAE and laboratory abnormalities.
4. Obtain a serum sample for PK analysis if requested by the Medical Monitor (determined on a case-by-case basis).
5. Document the quantity of the excess dose as well as the duration of the overdose in the CRF.

Decisions regarding dose modifications will be made by the Investigator in consultation with the Medical Monitor based on the clinical evaluation of the patient.

Parts 3 and 4 only: For this study, an overdose of pembrolizumab will be defined as any dose of 1000 mg or greater.

No specific information is available on the treatment of overdose of pembrolizumab. In the event of overdose, the participant should be observed closely for signs of toxicity. Appropriate supportive treatment should be provided if clinically indicated.

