Based on review of DLTs, the DMC may initiate step-dosing to improve the tolerability of NL-201, wherein 1 or more step-doses below the target dose would be provided prior to reaching the target dose (see Section 6.2.1.4). If step-dosing is used, the DLT window would extend from the first dose to 21 days after receiving the target dose (ie, would include the initial reduced-dose cycles in addition to the first target-dose cycle). Once a patient receives the intended target dose for their cohort, subsequent doses for that patient will continue at that dose level unless a delay in dosing of > 6 weeks causes washout of the drug, in which case the step-dosing regimen would be repeated if the patient is to resume dosing.

The DMC will determine the RP2D and treatment schedule (either A or B) for Part 2 by considering the PK, PDn, safety and tolerability, antitumor activity, and the occurrence of any cumulative toxicities over multiple cycles of NL-201.

Part 3 (NL-201 in Combination with Pembrolizumab)

Schedule A: Dosing of pembrolizumab and NL-201 will occur on Day 1 of each 21-day cycle. A fixed dose of 200 mg pembrolizumab will be administered before NL-201. NL-201 infusion will start 30-60 minutes after pembrolizumab infusion is complete.

Schedule B: Dosing of pembrolizumab will occur on Day 1 of each 21-day cycle. Dosing of NL-201 will occur on Day 1 and Day 8 of each 21-day cycle. On Day 1, a fixed dose of 200 mg pembrolizumab will be administered before NL-201. NL-201 infusion will start 30-60 minutes after pembrolizumab infusion is complete.

Combination Cohorts (21-day cycles)				Maximum dose of NL-201 that may be administered at 1 time (µg) ^a
Schedule A (D1)	Schedule B (D1+D8)	Pembrolizumab (D1)	NL-201 dose level (µg/kg)	
Planned NL-201 Dose Level				
P-1A	P-1B	200 mg	0.3	30
P-2A	P-2B	200 mg	1	100
P-3A	P-3B	200 mg	3	300
P-4A	P-4B	200 mg	6	600
P-5A	P-5B	200 mg	12	1200

Potential NL-201 Intermediate Dose Level^b				
P-2A-1	P-2B-1	200 mg	0.6	60
P-3A-1	P-3B-1	200 mg	1.5	150
P-3A-2	P-3B-2	200 mg	2.0	200
P-4A-1	P-4B-1	200 mg	4.0	400
P-4A-2	P-4B-2	200 mg	5.0	500
P-5A-1	P-5B-1	200 mg	7.5	750
P-5A-2	P-5B-2	200 mg	9.0	900
P-5A-3	P-5B-3	200 mg	10.0	1000

D = day; DMC = Data Monitoring Committee

- a Applicable to patients that weigh ≥ 100 kg (dose is capped as to not allow > 100 times the current dose level to be administered to a patient at 1 time)

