Planned NL-201 Dose Levels^b			
1A	1B	0.1	10
2A	2B	0.3	30
3A	3B	1.0	100
4A	4B	3.0	300
5A	5B	6.0	600
6A	6B	12.0	1200
Potential NL-201 Intermediate Dose Levels^b			
2A-1	2B-1	0.6	60
3A-1	3B-1	1.5	150
3A-2	3B-2	2.0	200
4A-1	4B-1	4.0	400
4A-2	4B-2	5.0	500
5A-1	5B-1	7.5	750
5A-2	5B-2	9.0	900
5A-3	5B-3	10.0	1000

D = day; DMC = Data Monitoring Committee; IV = intravenous.

a Applicable to patients that weigh ≥ 100 kg (dose is capped as to not allow > 100 times the current dose level to be administered to a patient at 1 time).

b At the recommendation of the DMC or based on Sponsor's determination, additional dose levels may be tested and/or cohorts may be expanded.

The maximum tolerated dose (MTD) is defined as the highest dose for which the probability of a patient experiencing a DLT with NL-201 during Cycle 1 is $\leq 33\%$. At the discretion of the DMC, and in keeping with the pre-specified mTPI design matrix, additional dose levels may be tested to determine the MTD.

Based on review of DLTs, the DMC may initiate step-dosing to improve the tolerability of NL-201, wherein 1 or more step-doses below the target dose would be provided prior to reaching the target dose (see Section 6.2.1.4). If step-dosing is used, the DLT window would extend from the first dose to 21 days after receiving the target dose (ie, would include the initial reduced-dose cycles in addition to the first target-dose cycle). Once a patient receives the intended target dose for their cohort, subsequent doses for that patient will continue at that dose level unless a delay in dosing of > 6 weeks causes washout of the drug, in which case the step-dosing regimen would be repeated if the patient is to resume dosing.

Supported by the mTPI design, the DMC will determine the RP2D and treatment schedule (IV Schedule A, IV Schedule B) for Part 2 by considering the PK, PDn, tolerability, antitumor activity, and the occurrence of any cumulative toxicities over multiple cycles of NL-201.

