6.2.1.4 Step-Dosing

Pre-clinical studies of NL-201 suggest that symptomatic toxicity of NL-201 in animals peaks with the first dose, such that symptomatic toxicity caused by subsequent doses is attenuated compared to that caused by the first dose. Dose levels that are not tolerated when given as an initial dose become tolerated after giving 1 or more initial step-doses at a reduced (tolerated) dose level, and remain tolerated in subsequent doses. Thus, if a specific dose level is not well tolerated (ie, elicits DLTs in $\geq 33\%$ of patients), it is possible that tolerability can be improved by providing 1 or more reduced doses. Once the target dose is reached, subsequent doses would be given at the expected dose level for that cohort.

If step-dosing is implemented, dosing during the first cycle of step-dosing will be administered on Day 1 and Day 8 for both Schedule A and Schedule B patients, though in subsequent cycles Schedule A patients will resume Q3W dosing while Schedule B patients will continue Day 1+8 dosing.

The Cycle 1 dose used for step-dosing will be calculated as one half of the highest tolerated initial dose (HTID), ie, the highest initial dose at which $< 33\%$ of patients experience DLTs. Subsequent cycles will increase 1 dose level (DL) at a time to the CTD.

Table 10 Step-Dosing Guidance

Steps	Cycle 1				
	D1	D8	C2	C3	C4
1	0.5 x HTID	0.5 x HTID	CTD		
2	0.5 x HTID	0.5 x HTID	HTID + 1 DL	CTD	
3	0.5 x HTID	0.5 x HTID	HTID + 1 DL	HTID + 2 DL	CTD

C = cycle; CTD = cohort target dose; D = day; DL = dose level; HTID = highest tolerated initial dose

The DLT window for each patient during step-dosing will extend to include the cycle in which the patient first receives the CTD. The DLT window for each cohort is highlighted in gray in [Table 10](#).

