Dyspnea		Hold dose until Grade ≤ 2 , resume 1 dose level lower. Stop treatment if ventilator support is required
Oliguria		Hold dose until Grade ≤ 2 , resume 1 dose level lower
Increased creatinine		Hold dose until Grade ≤ 2 , resume 1 dose level lower if peak is Grade 3, stop treatment if peak is Grade 4.
Renal failure		Stop therapy if requires dialysis
Pleural effusion		Hold dose until Grade ≤ 2
Bowel perforation		Stop treatment
Anxiety		Hold dose until Grade ≤ 2 or back to baseline, resume 1 dose level lower

Potential Toxicity	Dose Modification if Grade ≤ 2	Dose Modification if Grade ≥ 3
Confusion		Hold dose until Grade ≤ 2, resume 1 dose level lower
Agitation or combativeness		Hold dose until Grade ≤ 2, resume 1 dose level lower
Somnolence		Hold dose until Grade ≤ 2, resume 1 dose level lower
Insomnia		No change
Arrhythmia		Hold dose until Grade ≤ 2, resume 1 dose level lower. If not resolved back to baseline within 3 weeks, or normal sinus rhythm not achieved with chemical cardioversion, stop treatment.
Elevated troponin levels		Hold dose until Grade ≤ 2, resume 1 dose level lower. If changes in left ventricular function have not improved to baseline within 3 weeks, stop treatment.
Myocardial infarction		Stop treatment
Elevated transaminases ^b		Hold dose if Grade 4 without liver metastases. If changes have not improved to baseline within 3 weeks, stop treatment.
Hyperbilirubinemia		Hold dose if Grade 4 without liver metastases. If changes have not improved to baseline within 3 weeks, stop treatment.
Electrolyte imbalances		Hold dose until Grade ≤ 2
Neutropenia		Hold dose until Grade ≤ 2, resume 1 dose lower if ANC < 500 for ≥ 5 days
Febrile neutropenia		Stop treatment

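### The NL-201 overdose rule in Section 8.5 is written as 20% of target instead of 20% above it, and does not say which dose is the target

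*Combined protocol and SAP*

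**What the plan says.** Section 8.5 states that "any dose of NL-201 greater than 20% of target dose within a 24-hour time period will be considered an overdose". The definition sets several duties in motion. "Any overdose of the Sponsor's product, as defined below, should be reported to the Sponsor within 24 hours of awareness", whether or not there are symptoms or laboratory changes. The investigator must contact the Medical Monitor at once, consider supportive care, monitor closely, and draw a PK sample if asked. Step 5 reads "Document the quantity of the excess dose as well as the duration of the overdose in the CRF". Section 8.5 neither defines the target dose nor refers to a definition. For pembrolizumab, by contrast, it gives a fixed amount of 1000 mg or more.

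Elsewhere the term belongs to step-dosing. The Synopsis (1.1) describes a scheme "wherein 1 or more step-doses below the target dose would be provided prior to reaching the target dose". Section 6.2.1.1 has the clause "Once a patient receives the intended target dose for their cohort", and Section 6.2.1.2 follows the same usage. Section 6.2.1.4 and Table 10 set the Cycle 1 dose (Days 1 and 8) at half the highest tolerated initial dose (HTID), then raise it one level at a time to the cohort target dose (CTD). The stated reason is: "Dose levels that are not tolerated when given as an initial dose become tolerated after giving 1 or more initial step-doses". For dose reductions, several entries in Table 11 tell the site to "resume 1 dose level lower".

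**The concern.** The first fault is in the wording: the rule says of target where it should say above target, so a correct dose meets it.

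The second is in the reference dose. Inserting the missing word does not tell a site what to compare against. For a step-dosed patient, the dose due in Cycle 1 and the cohort's target are different numbers. Measured against the cohort's target, giving the full target as the first dose is no overdose at all, although that is the exposure step-dosing exists to avoid. A dose-reduced patient who is given the former dose could be missed in the same way, if the target is not reset after the reduction; the text leaves that open too.

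At stake is whether a multi-fold first-dose error with a first-in-human cytokine agonist triggers the Section 8.5 steps, and whether two sites would classify the same event alike.

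**Working it through.** The plan gives no worked figure to reproduce, so the check applies each reading of the rule to the protocol's own doses.

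**Inputs**
- Planned levels (Table 8): 0.1, 0.3, 1, 3, 6, 12 µg/kg.
- Full ladder with Table 8 intermediates: 0.1, 0.3, 0.6, 1, 1.5, 2, 3, 4, 5, 6, 7.5, 9, 10, 12 µg/kg.
- First step-dose = 0.5 × HTID (Table 10).
- Assumption, from Section 6.2.1.4: the CTD is one level above the last step, so one step means CTD = HTID + 1 level and three steps mean CTD = HTID + 3 levels.

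**Worked case: HTID 3, CTD 6, first step-dose 0.5 × 3 = 1.5 µg/kg**

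| Given | Due | Literal, limit 0.20 × 6 = 1.2 | 20% above CTD, limit 1.2 × 6 = 7.2 | 20% above dose due |
|---|---|---|---|---|
| 6.0 | 6.0 | flagged (wrongly) | not flagged | not flagged (limit 7.2) |
| 1.5 | 1.5 | flagged (wrongly) | not flagged | not flagged (limit 1.8) |
| 6.0 | 1.5 | flagged | **not flagged** | flagged (limit 1.8) |

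**Literal reading, other doses**
- A dose reduced by one planned level is 0.1/0.3 = 33.3%, 0.3/1 = 30.0%, 1/3 = 33.3%, 3/6 = 50.0% or 6/12 = 50.0% of the cohort dose. All exceed 20% if the target stays at the cohort level.
- Step-doses vary: 1.5/6.0 = 25% is flagged, but 0.5/12.0 = 4.2% is not.

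**20%-above-CTD reading: full CTD given in place of the first step-dose.** The dose is always 100% of target, so it is never flagged. Error multiple = CTD / (0.5 × HTID):
- One step, planned levels: 0.3/0.05 = 6.0; 1/0.15 = 6.67; 3/0.5 = 6.0; 6/1.5 = 4.0; 12/3 = 4.0. Range 4.0 to 6.7.
- One step, full ladder: from 10/4.5 = 2.2 to 0.3/0.05 = 6.0.
- Three steps, planned levels: 3/0.05 = 60; 6/0.15 = 40; 12/0.5 = 24. Range 24 to 60.
- Three steps, full ladder: from 12/3.75 = 3.2 to 1.0/0.05 = 20.

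**Dose-reduced patient given the former dose, target not reset.** Multiple = former / reduced dose:
- Planned levels: 6/3 = 2.0 to 1/0.3 = 3.3.
- Full ladder: 10/9 = 1.11 to 0.3/0.1 = 3.0.
- Where the levels are close (6/5, 9/7.5 and 12/10 = 1.2; 10/9 = 1.11), even a rule of more than 20% above the dose due would not flag the error.

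**The case against.** The strongest reply is that this is a drafting slip with little practical consequence. The section is about overdose and step 5 asks for the excess, so no site would report a correct dose. The step-dosing fault needs several things together: the DMC opts for step-dosing, the site takes target to mean the cohort's dose, the wrong dose passes the second-person check in Section 6.4, and the error stays at or below 120% of the CTD. Patients would also be watched closely anyway. Table 7 requires 24 hours in hospital after the first dose and initially 8 hours after later ones. Tables 3 and 4 already schedule serial PK, cytokines and safety laboratory tests around the Cycle 1 doses. Section 8 asks for immediate discussion of urgent safety concerns, and any resulting serious event is reportable within 24 hours. The largest multiple, 60, requires an HTID of 0.1 µg/kg, meaning that 0.3 was not tolerated as a first dose; nothing in the documents suggests that.

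Much of this stands. The intent behind the first fault is clear, the second is conditional, and the scheduled observation and sampling reduce what is lost. The 24- to 60-fold range applies only to three steps on the planned levels. What does not stand is that the rule can be left alone. No text corrects it, and the reading that misses the error is the one the protocol's own vocabulary supports. Section 8.5 is the provision that expressly calls for a 24-hour report of a dosing error that has caused no symptoms. The Section 6.4 check and the source verification in Section 10.1.8 make an error less likely but do not classify one that occurs.

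**Conclusion.** Both faults hold. The wording fault is unconditional: the threshold as printed makes every correct full-target dose an overdose. The reference fault is conditional on step-dosing being used and on target carrying its usual meaning in this protocol. The unflagged one-step error is then 4.0- to 6.7-fold on the planned levels, or 2.2- to 6.0-fold if every intermediate level is used; more steps give larger multiples. The dose-reduction case needs the further assumption that the target is not reset. The consequence is limited to safety reporting and monitoring, mainly the 24-hour report and Medical Monitor contact for a non-serious dosing error. The rule should be corrected, but it does not bear on the design, the sample size or the analysis.

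**What to change.** Replace the sentence in Section 8.5 with wording such as: *An NL-201 overdose is an amount given within 24 hours that is more than 20% above the dose assigned to that patient for that administration. The assigned dose takes account of step-dosing, any dose reduction and the weight cap.* Bring any matching instruction on the safety form or CRF into line; those forms are not reproduced in the protocol.

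Tying the limit to the assigned dose mends both faults: a correct dose can never be flagged, and the full CTD given at the first step visit always is. If the sponsor also wants to catch former-dose errors between levels 1.2-fold apart or less, it needs a tighter percentage or a separate rule for any wrong-level dose.

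The cost is one sentence and the matching form text. It can go into the next amendment, with the IRB/IEC approval that Section 10.1.1 requires.

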8.6 Pharmacokinetics

Serial serum samples for PK analysis of NL-201 will be collected during Cycles 1 and 2 for IV Schedule A, IV Schedule B. In addition, trough samples (ie, pre-dose) and peak samples (ie, 1 hour after dosing) will be collected at prespecified time points as described in the Schedule of Events ([Section 1.3](#)). The primary purpose of collecting these samples is to measure the serum concentrations of NL-201 to characterize the PK of NL-201 after single- and multiple-dose administration. This information will also further inform the building of PK models to describe NL-201 PK and such models will be used to predict NL-201 serum levels under different dosing scenarios to help select an appropriate dose/schedule of NL-201. The dates and exact times of NL-201 administration before collecting PK samples and the dates and exact times of post-dose PK sample collections will be recorded. PK characterization will assess both NL-201 and the free protein.

8.7 Pharmacodynamics/Biomarkers

8.7.1 Exploratory Assessment of NL-201-Dependent Effects in Blood

Blood samples will be collected as indicated in the Schedule of Events ([Section 1.3](#)) to assess the PDn effect of NL-201 during therapy. Planned assays include flow-cytometric analysis on PBMCs as well as serum measurements of inflammatory cytokines.

8.7.2 Exploratory Assessment of NL-201-Dependent Effects on the Tumor Microenvironment (Patients who Have Consented to Tumor Biopsy Collection Part 1, Part 2 and Part 4)

To understand the relationship between the biological characteristics of tumors before treatment and patient outcomes, tissue from pre-treatment (archival or freshly obtained specimens) and on-treatment tumor biopsies will be examined. Biopsies will be assessed for specific PD,

predictive, and prognostic biomarkers in the tumor. To characterize the malignancy and response to study treatment, biomarker assessments in tumor biospecimens may include measurements of NL-201 potential metabolites, PD-L1, as well as characterization of the TME, drug target(s), tumor subtyping, and/or gene expression. Assays may include immunohistochemistry (IHC) and next generation sequencing of ribonucleic acid (RNA) and deoxyribonucleic acid (DNA).

Tumor biopsies should be performed as indicated in the Schedule of Events (**Section 1.3**). Biopsies should be collected by appropriately trained clinical site personnel (eg, an interventional radiologist for internal tumor biopsies; trained personnel such as a dermatologist for cutaneous tumor biopsies). It is strongly recommended that a pathologist be present during biopsies when feasible to ensure sufficient tumor content of the biopsy location, and to confirm that biopsy acquisition and processing techniques are optimal.³⁴

Tumor biopsies will be collected for the assessment of NL-201-mediated effects on the tumor microenvironment (TME), including paired pre- and post-treatment biopsies. Biopsy tissues for exploratory analysis should be in FFPE blocks when possible, and secondarily as slides. Analyses will include, but will not necessarily be limited to, transcriptional profiling and multiplex immunohistochemistry and to assess treatment-related changes in immune cell populations, phenotypes and spatial organization within the TME.

8.7.3 PD-L1 Expression (Part 4 Only)

Tumor tissue (archival or fresh biopsy) will be collected at screening to assess PD-L1 expression.

8.7.4 Tumor Mutational Burden Determination (Part 4 Only)

Tumor tissue (archival or fresh biopsy, as available) will be collected at screening to assess tumor mutational burden (TMB).

8.8 Immunogenicity Assessments

Antibodies to NL-201 will be evaluated in blood samples collected from all patients according to the Schedule of Events. These samples will be tested by the Sponsor's designee.

Blood samples will be screened for antibodies binding to NL-201 and the titer of confirmed positive samples will be reported. Other analyses may be performed to verify the stability of antibodies to NL-201 and/or further characterize the immunogenicity of NL-201.

The detection and characterization of antibodies to NL-201 will be performed using a validated assay method under the supervision of the Sponsor. All samples collected for detection of antibodies to study drug will also be evaluated for NL-201 serum concentration to enable interpretation of the antibody data. Antibodies may be further characterized and/or evaluated for their ability to neutralize the activity of the study drug(s).

9 STATISTICAL CONSIDERATIONS

9.1 Statistical Hypothesis

For NL-201 monotherapy (Parts 1 and 2), no statistical hypothesis will be tested during dose escalation in Part 1. In Part 2, the null hypothesis that the response rate to NL-201 is $\leq 2.5\%$ in each cohort will be tested against the alternative hypothesis that the response rate is $\geq 15\%$.

For NL-201 in combination with pembrolizumab (Parts 3 and 4), no statistical hypothesis will be tested during dose escalation in Part 3 and dose expansion in Part 4.

9.2 Sample Size Determination

In Part 1, 2 NL-201 monotherapy dosing schedules (IV Schedule A, IV Schedule B) will be evaluated with the goal being to determine the MTD of each schedule. The MTD is defined as the highest dose for which the probability of a patient experiencing a DLT with NL-201 is $\leq 33\%$. Based on the totality of data arising in Part 1, the DMC will determine a RP2D and treatment schedule of NL-201 for Part 2 that will not exceed the MTD.

Dose escalation in Part 1 will be guided by an mTPI design with up to approximately 50 enrolled per schedule as depicted in [Figure 5](#). This design and number of patients per schedule provides a high likelihood of correctly identifying the MTD with approximately one half of the patients (ie, approximately $n = 15$) being exposed to the MTD, very few being exposed to lower, less effective doses and relatively few being exposed to the MTD+1 dose.

In addition, there will be backfill cohorts (up to approximately 12 patients in total), at certain DMC-cleared dose levels and schedules, to collect, pharmacokinetic, pharmacodynamic and response data in certain tumor types or to explore additional pre-medication regimens (eg. steroids). The decision to enroll patients into backfill cohorts and to define the patients to be enrolled will be made by the Sponsor.

Note: “Enrolled” means any patient that has met all of the study inclusion and exclusion criteria and is eligible to receive study drug.

In Part 2, an expansion cohort study will evaluate safety and estimate antitumor activity of NL-201 as a monotherapy at the RP2D in 2 cohorts of patients: (1) melanoma and (2) RCC. A Simon’s 2-stage design will be used for each cohort independently to test the null hypothesis that the true monotherapy response rate is $\leq 2.5\%$ vs the alternative that the true response rate is $\geq 15\%$. In the first stage, 18 patients will be evaluated. If 0/18 objective responses are seen, recruitment to the cohort will be stopped for futility. Otherwise, a further 12 patients will be evaluated for a total of 30 patients. This design provides 80% power and a Type I error rate of 0.031 under the stated null and alternative hypotheses.

In Part 3, with the mTPI study design, the exact number of patients needed to complete the dose escalation is unknown because it depends on the number of cohorts required to reach MTD and the number of patients in each cohort. Dose escalation will be conducted in up to 42 adult

patients (21 patients in each schedule) with advanced solid tumors to determine the safety profile, RP2D and treatment schedule of NL-201 in combination with pembrolizumab.

No formal hypothesis test is planned for Part 4 (dose expansion). The sample size of 30 is considered appropriate and sufficient to confirm the combination RP2D. The sample size for each cohort was based on the consideration of precision of estimates of ORR. For a sample size of 30, below is the summary of expected precision of ORR estimates. For example, if there is 6 responders observed among 30 patients treated, the observed ORR will be 20%, with 95% confidence interval of (7.7%, 38.6%).

Table 14 Observed ORR and 95% Confidence Interval with a Sample Size of 30

Number of Responders	Observed ORR	95% Confidence Interval*
6	20%	(7.7%, 38.6%)
9	30%	(14.7%, 49.4%)
12	40%	(22.7%, 59.4%)

ORR = objective response rate
 * Based on Clopper-Pearson method (1934)

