9.4 Statistical Analyses

9.4.1 General Considerations

Demographic data and disease-related characteristics will be summarized separately for Part 1, by schedule (eg, IV Schedule A, IV Schedule B), and Part 2, by expansion cohort. Descriptive statistics (count and percent, mean, median, standard deviation, minimum, maximum) will be used. All patient data, efficacy and safety data will be summarized. Data from Parts 3 and 4 (NL-201 in combination with pembrolizumab) will be summarized in a similar manner.

A full Statistical Analysis Plan will be prepared to describe in full the statistical methods and analyses to be applied to the data arising in this study.

9.4.2 Determination of MTD in Part 1 and Part 3

For each schedule (IV Schedule A, IV Schedule B) in Part 1 (NL-201 monotherapy), the determination of MTD will be the highest dose for which the probability of a patient experiencing a DLT with NL-201 during Cycle 1 is $\leq 33\%$. Refer to [Section 9.2](#) for more details.

Similarly, for each schedule separately in Part 3 (NL-201 in combination with pembrolizumab), the determination of MTD will be the highest dose for which the probability of a patient experiencing a DLT with NL-201 during Cycle 1 is $\leq 33\%$. Refer to [Section 9.2](#) for more details.

9.4.3 Assessment of Preliminary Efficacy in Part 2 and Part 4

For NL-201 monotherapy, while tumor response data based on both RECIST 1.1 and iRECIST will be collected from all patients in dose escalation and expansion, formal analysis of tumor response will only be performed for the expansion cohorts in Part 2 based on iRECIST. Results will be presented and summarized using an exact 95% binomial confidence interval.

Other response-related efficacy parameters including time to response, duration of response, and clinical benefit rate will be also summarized by Part 2 expansion cohort.

In expansion cohorts in Part 2, OS and progression free survival (defined as the time from study entry to the time of disease progression or death from any cause) will be displayed graphically using Kaplan-Meier plots. Median PFS and OS will be extracted from the Kaplan-Meier plots along with their associated 95% confidence intervals. PFS and OS rates at 3 monthly intervals will also be extracted. Patients who do not experience progression or death will be censored at their last clinic visit contact for the assessment of disease progression.

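### Part 2 Simon design: the stated 80% power and 0.031 type I error do not follow from 18 + 12 = 30 patients at any final cut-off, and no final cut-off is given

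*Combined protocol and SAP*

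**What the plan says.** Section 9.1 limits formal hypothesis testing to Part 2. There, a null response rate of at most 2.5% "in each cohort will be tested against the alternative hypothesis that the response rate is" at least 15%. Section 9.2 applies a Simon two-stage design to the melanoma and RCC cohorts independently:

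- Stage 1: "In the first stage, 18 patients will be evaluated".
- Futility: "If 0/18 objective responses are seen, recruitment to the cohort will be stopped for futility".
- Stage 2: "Otherwise, a further 12 patients will be evaluated for a total of 30 patients".
- Operating characteristics: "This design provides 80% power and a Type I error rate of 0.031 under the stated null and alternative hypotheses".

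The paragraph ends there. Section 9.4.3 adds that "formal analysis of tumor response will only be performed for the expansion cohorts in Part 2 based on iRECIST" and that results will be shown with an exact 95% binomial confidence interval. It gives no decision rule. The synopsis and Section 4.1 name the Simon design and the maximum of 30 per cohort but no rejection number. Section 9.4.1 announces a full Statistical Analysis Plan, which is not part of the document.

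**The concern.** A Simon two-stage design has two boundaries: one for stopping after stage 1 and one for rejecting the null at the end. Only the first is given here. With the response rates, stage sizes and futility bound fixed, the type I error and power depend on the final cut-off alone. It should therefore be possible to recover the cut-off from the quoted 0.031 and 80%, but no cut-off produces them.

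Two things are at stake. A reader cannot tell how many responses in a cohort count as success, in an open-label study where that rule should be fixed before responses are seen. And the quoted error rates are not those of the design that will be run.

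**Working it through.** **Inputs (Section 9.2):** null rate p0 = 0.025; alternative p1 = 0.15; stage 1 n1 = 18, stop at 0; stage 2 n2 = 12; total 30. The test is one-sided, as the direction of the hypotheses implies.

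**Formula.** With X1 ~ Bin(18, p) and X2 ~ Bin(12, p), the null is rejected at cut-off c if X1 ≥ 1 and X1 + X2 ≥ c. So

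P(reject) = P(Bin(30, p) ≥ c) − (1 − p)^18 × P(Bin(12, p) ≥ c).

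The second term removes paths that would have reached c but were stopped at 0/18.

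**Early stopping:** 0.975^18 = 0.634 under the null; 0.85^18 = 0.0536 under the alternative.

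**Worked case, c = 3:**

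- Type I error: 0.03839 − 0.63399 × 0.002902 = 0.03839 − 0.00184 = 0.0366 (0.03655 before rounding).
- Power: 0.84860 − 0.05365 × 0.26418 = 0.84860 − 0.01417 = 0.8344.

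**All relevant cut-offs, 18 + 12 = 30:**

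| Reject if responses ≥ | Type I error at 2.5% | Power at 15% |
|---|---|---|
| 1 | 0.366 | 94.6% |
| 2 | 0.150 | 92.2% |
| 3 | 0.0366 | 83.4% |
| 4 | 0.0063 | 67.3% |
| 5 | 0.0008 | 47.4% |
| 6 | 0.0001 | 28.9% |

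Both columns keep falling beyond this. The stated 0.031 lies between the rows for 3 and 4, and so does 80%. The plan's own figures are not reproduced.

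**Other readings tried:**

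- Single stage of 30, at least 3: 0.0384 and 84.9%.
- Stop at 1 or fewer of 18, at least 3/30: 0.0263 and 74.0%.
- Null of 5% with 18 + 12: type I error 0.180 at 3 or more, 0.060 at 4 or more.
- Error over both cohorts at 3 or more: 1 − (1 − 0.03655)² = 0.072.

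None gives the stated pair.

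**What would give it.** Keep the stated first stage (18, stop at 0) and search totals from 19 to 60 with cut-offs 1 to 8. Only one design rounds to 0.031 and 80%: 18 + 10 = 28, success at 3 or more.

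- Type I error: 0.03213 − 0.63399 × 0.001643 = 0.0311.
- Power: 0.81292 − 0.05365 × 0.17980 = 0.8033.

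If the total is instead held at 30 and the first stage varied (stop at 0, 1 or 2), only 21 patients with a stop at 1 or fewer and success at 3 or more fits (0.0314 and 79.5%). That contradicts the stated 18 and 0/18.

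**Expected size under the null, 18 + 12:** 18 + 12 × (1 − 0.634) = 22.4 patients per cohort.

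**The case against.** The arithmetic is not in dispute; the case on the other side concerns weight and remedy.

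- *80% may mean at least 80%.* On that reading the power claim is true at 3 or more of 30 (83.4%). This stands, but it rescues only the power figure: 0.0366 does not round to 0.031.
- *Response rate is a secondary endpoint.* The primary objectives of Parts 1 and 2 are safety and the recommended dose (Section 3), and the futility stop is stated clearly. This also stands. The mismatch changes neither enrolment nor the stage 1 stop, which limits the seriousness of the point.
- *The Statistical Analysis Plan may give the cut-off.* It may, but it cannot make 0.031 correct for 18 + 12, and error rates quoted in the protocol should follow from a rule the protocol states.
- *Naming 3 of 30 chooses the rule for the sponsor, and Section 9.4.3 could suggest another.* The two-sided Clopper-Pearson lower limit is 2.1% at 3/30, below the 2.5% null, and 3.8% at 4/30, above it. A reader who used the interval as the test would need 4 responses, with power of 67%. However, Section 9.4.3 offers the interval as a summary and does not make it the test, and a cut-off of 4 would fall well short of the stated 80% power. The possible disagreement at exactly 3 responses is worth a sentence in the plan.

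**Conclusion.** The concern holds. For the design described, no final cut-off gives a type I error of 0.031 with 80% power, and the document states no final cut-off.

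The numerical error is small. Under the natural rule of 3 or more of 30, type I error exceeds the stated value by about 0.006 (0.0366 against 0.031), and power is 3.4 points above the claim. That rule is the only one with power of at least 80% and type I error below 0.05; the 0.05 limit is an assumption, since the plan gives no nominal level. On that basis 30 patients per cohort is adequate.

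The larger gap is the missing rule: 3 against 4 responses means power of 83.4% against 67.3%, and a cohort with exactly 3 responders could be called either way.

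The stated figures fit a total of 28 patients, but the document never mentions 28, so that origin is only a possibility and the conclusion does not depend on it. The results assume exact binomial calculation, a one-sided test, and all 18 and 30 patients evaluable.

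**What to change.** In Section 9.2, replace the last sentence of the Part 2 paragraph with: *H0 is rejected if at least 3 of 30 patients respond. This design has a type I error rate of 0.037, power of 83% and a probability of early stopping under H0 of 0.63.* Carry the same cut-off into the Statistical Analysis Plan, and note there that the exact 95% interval is descriptive and that at 3/30 it still includes 2.5%.

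If the sponsor did intend 0.031 and 80%, the consistent alternative is to state 10 patients in stage 2, a total of 28, and rejection at 3 or more. The patient numbers in the synopsis and Sections 4.1 and 4.1.2 would then change as well.

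The first option costs one sentence in the protocol and its repetition in the analysis plan. Patient numbers and analysis methods stay as they are.
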